8.3.5 Other

8.3.5.1 28-joint Count (SJC and TJC)

The 28-joint count will be performed for swollen and/or tender joints in the following: shoulder, elbow, wrist, MCP and PIP, and knee. Joint swelling is defined as soft tissue swelling that is detectable along the joint margins. Joint tenderness is defined as the presence of pain in a joint at rest with pressure or on movement of the joint (Scott 1996). This assessment will be used as an input parameter for 2010 ACR/EULAR Classification Criteria (Section 8.3.1), DAS28 score (Section 8.3.2), and CDAI score (Section 8.3.3).

Patient Global Assessment of Disease Activity

Patient global assessment of disease activity will be evaluated using a 10-point scale wherein a score of 0 is considered 'very well' and score of 10 is considered 'very poor'. Score intervals are 0.5 apart (yielding 20 possible options -0, 0.5, 1.0, 1.5...20). This assessment will be used as an input parameter for CDAI score (Section 8.3.3) and ACR Response Criteria (Section 8.3.4).

Provider Global Assessment of Disease Activity

Provider global assessment of disease activity will be evaluated using a 10-point scale wherein a score of 0 is considered 'very well' and score of 10 is considered 'very poor'. Score intervals are 0.5 apart (yielding 20 possible options -0, 0.5, 1.0, 1.5...20). This assessment will be used as an input parameter for CDAI score (Section 8.3.3) and ACR Response Criteria (Section 8.3.4).

8.3.5.2 Patient Assessment of Pain (VAS)

Patient assessment of pain will be evaluated using the visual analog scale (VAS). Using a ruler, the score will be determined by measuring the distance (mm) on the 10-cm line between the 'no pain' anchor and the patient's mark, providing a range of scores from 0 to 100. This assessment will be used as an input parameter for DAS28 score (Section 8.3.2) and ACR Response Criteria (Section 8.3.4).

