4.1.1 Inclusion Criteria

Each subject must meet the following criteria to be enrolled in this study.

- 1. The subject has provided written informed consent with HIPAA (Health Information Portability and Accountability Act) authorization before the initiation of any study-related procedures.
- 2. The subject is at least 18 years of age and was ≥ 18 years of age at the time of RA diagnosis.
- 3. The subject is a candidate for initiation of, or change to, a new anti-TNF α bDMARD therapy.
- 4. The subject has RA as determined by the 2010 American College of Rheumatology/European League Against Rheumatism (ACR/EULAR) Classification Criteria (score of $\geq 6/10$).
- 5. The subject has moderate to severe RA as determined by a 28-joint disease activity score (DAS28) of ≥ 3.2 (includes the Erythrocyte Sedimentation Rate [ESR] test and Visual Analog Scale [VAS]).
- 6. Subjects receiving traditional DMARDs must have been on therapy for ≥ 90 days and at a stable dose for ≥ 30 days prior to the first imaging visit (Day 0).
- 7. Subjects receiving bDMARD or janus kinase (JAK) inhibitor therapy must have been at a stable dose > 60 days prior to the first imaging visit (Day 0).
- 8. If the subject is receiving NSAIDS (nonsteroidal anti-inflammatory drug) or oral corticosteroids, the dose has been stable for > 28 days prior to the first imaging visit (Day 0). The corticosteroid dose must be ≤ 10 mg/day of prednisone or an equivalent steroid dose.

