8.3.2 DAS28 Evaluation

Subjects will be evaluated for the DAS28 (Prevoo 1995) at the following timepoints: screening (Day -30 to -1), Visit 4 (5 \pm 1 weeks post-initiation of new anti-TNF α bDMARD), Visit 6 (12 \pm 1 weeks post-initiation of new anti-TNF α bDMARD), and Visit 8 (24 \pm 1 weeks post-

initiation of new anti-TNFα bDMARD). DAS28 evaluations may be completed up to 30 days before imaging Visit 2 and up to 7 days before imaging Visits 4, 6, and 8.

DAS28 is calculated from 4 components: Tender Joint Count (TJC), Swollen Joint Count (SJC), visual analogue scale (VAS) of the subject's global health, and the laboratory parameter erythrocyte sedimentation rate (ESR), such that:

$$DAS28 = 0.56\sqrt{TJC} + 0.28\sqrt{SJC} + 0.7\ln(ESR) + 0.014(VAS)$$

A DAS28 score of higher than 5.1 is indicative of high disease activity whereas a DAS28 below 3.2 indicates low disease activity. A subject with a DAS28 lower than 2.6 is considered to be in remission. For consistent scoring, the following calculator should be utilized: https://qxmd.com/calculate/. See Appendix 3 for details.

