Appendix 3 DAS28 Scale

DISEASE ACTIVITY SCORE IN 28 JOINTS (DAS28)

The DAS28 is a frequent outcome measure used in therapeutic trials and is also used to guide treatment decisions and describe disease activity across populations. It is the basis for several other RA measurement tools, including the EULAR response criteria.

FORM A		LEFT		RIGHT	
		SWOLLEN	TENDER	SWOLLEN	TENDER
Shoulder					
Elbow					
Wrist					
Metacarpophalangeal (MCP)	1				
	2				
	3				
	4				
	5				
Proximal Interphalangeal (PIP)	1				
	2				
	3				
	4				
	5				
Knee					
Subtotal					
TOTAL		SWOLLE	EN .	TENDE	٤

FORM B

Swollen (0–28)

Tender (0–28)

ESR (or CRP)

VAS disease activity (0–100mm)

DAS28=0.56*√(TENDER JOINTS) + 0.28*
√(SWOLLEN JOINTS) + 0.70*LN(ESR/CRP) + 0.014*VAS

By comparing a patient's DAS28 score over multiple time points, you can substantiate his/her improvement or response. The EULAR response criteria are defined as follows:

present das28	DAS28 IMPROVEMENT OVER TIME POINTS							
	>1.2	<0.6						
<3.2	good response	moderate response	no response					
3.2-5.1	moderate response	moderate response	no response					
>5.1	moderate response	no response	no response					

Source: DAS-Score.nl. Available at http://www.das-score.nl/www.das-score.nl/index.html. Accessed February 5, 2009.

HOW TO CALCULATE A DAS28 SCORE

- Perform a swollen and tender joint examination of your patient, noting each affected joint on Form A. When complete, add all of the swollen and tender joints and record the totals in the appropriate boxes on Form B.
- 2. Obtain and record the patient's erythrocyte sedimentation rate (ESR) in mm/h in the appropriate box on Form B. Note: C-reactive protein (CRP) levels may be used as a substitute for an ESR.
- 3. Obtain and record the patient's general health on a Visual Analog Scale (VAS) of 100 mm in the appropriate box on Form B. Note: DAS28 calculations may be performed without a VAS measurement.
- 4. Plug the appropriate values into the formula at the bottom of Form B (many online calculators are available to compute this value including http://www.das-score.nl/www.das-score.nl/dasculators.html).
- 5. A DAS28 score of higher than 5.1 is indicative of high disease activity, whereas a DAS28 below 3.2 indicates low disease activity. A patient is considered to be in remission if they have a DAS28 lower than 2.6.

Courtesy of http://www.iche.edu/newsletter/DAS28.pdf

[figure not shown]

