Patient No.	Visit	Date	Tender Joint Count	Swollen Joint Count	Patient's Global Disease Activity	Physician's Global Disease Activity	Patient Assessment of Pain	Patient Assessment Physical Function	Acute Phase Reactant Value	ACR20	ACR50	ACR70
XXXX	XXXXXXX	XXXXXXX	XXX	XXX	XXX	XXX	XXX	XXX	XXX	XXX	XXX	XXX
XXXX	XXXXXXX	XXXXXXX	XXX	XXX	XXX	XXX	XXX	XXX	XXX	XXX	XXX	XXX

Data Listing 19. CDAI, DAS28, HAQ-DI, and WPI Scores Data Listing Navidea Biopharmaceuticals - Study No. NAV3-33 Safety Population (N=xxx)

				CDAI	Component							
					Patient's	Physician's					HAQ-	
			Tender	Swollen	Global	Global	CDAI		DAS28		DI	WPI
Patient			Joint	Joint	Disease	Disease	Total	CDAI	Total	DAS28	Total	Total
No.	Visit	Date	Score	Score	Activity	Activity	Score	Improved	Score	Improved	Score	Score
XXXX	XXXXXXX	XXXXXXX	XXX	XXX	XXX	XXX	XXX	Х	XX.X	Х	XX.X	XX.X
XXXX	XXXXXXX	XXXXXXX	XXX	XXX	XXX	XXX	XXX	х	XX.X	х	XX.X	XX.X

Data Listing 20. DAS28 by Joint Data Listing Navidea Biopharmaceuticals - Study No. NAV3-33 Safety Population (N=xxx)

Patient No.	Visit	Date	Joint	Result (Right Body)	Result (Left Body)
****	******	******	*******	***	***
лллл	ллллллл	ллллллл	*****	XXX	XXX
			****	XXX	XXX
			*****	XXX	XXX
			XXXXXXXXX	XXX	XXX
XXXX	XXXXXXX	XXXXXXX	*****	XXX	XXX
			*****	XXX	XXX
			XXXXXXXXX	XXX	XXX
			XXXXXXXXX	XXX	XXX
			*****	XXX	XXX

DAS28 Joint Classification

Data Listing 21. DAS28 by Patient Data Listing Navidea Biopharmaceuticals - Study No. NAV3-33 Safety Population (N=xxx)

					DAS28		
					Patient	Erythrocyte	
			Tender	Swollen	VAS	Sedimentation	
Patient			Joint	Joint	Global	Rate (ESR;	DAS28
No.	Visit	Date	Count	Count	(mm)	mm/hr)	Score
XXXX	XXXXXXX	*****	XXX	XXX	XXX	XXX	XXX
XXXX	XXXXXXX	XXXXXXX	XXX	XXX	XXX	XXX	XXX

Data Listing 22. Vital Signs Data Listing Navidea Biopharmaceuticals - Study No. NAV3-33 Safety Population (N=xxx)

Patient	Vici+	Date	Time	Temp.	Systolic Blood Pressure	Diastolic Blood Pressure	Heart Rate (bpm)	Respirations
110.	VISIC	Date	TTING	(1)	(mining)	(Inning)	(upin)	per minuce
XXXX	XXXXXXX	XXXXXXX	XXXXX	XXX	XXX	XXX	XXX	XXX
			XXXXX	XXX	XXX	XXX	XXX	XXX
			XXXXX	XXX	XXX	XXX	XXX	XXX
XXXX	*****	*****	XXXXX	XXX	XXX	XXX	XXX	XXX
			XXXXX	XXX	XXX	XXX	XXX	XXX
			XXXXX	XXX	XXX	XXX	XXX	XXX

Data Listing 23. ECG Parameters Data Listing Navidea Biopharmaceuticals - Study No. NAV3-33 Safety Population (N=xxx)

Patient No.	Visit	Date	Time	Heart Rate (bpm)	PR Interval (msec)	QRS Interval (msec)	QT Interval (msec)	QTCF Interval (msec)	Overall Interpretation

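### Protocol 8.3.5.2 names the pain VAS as a DAS28 input, contradicting the DAS28 definition, which uses a patient global-health VAS; DAS28 eligibility near 3.2 and the secondary DAS28 analyses are exposed

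*Protocol*

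**What the plan says.** **The definition.** Protocol 8.3.2 lists four DAS28 components. The VAS component is the "visual analogue scale (VAS) of the subject's global health". Appendix 3, which 8.3.2 refers to, gives the scoring step: "Obtain and record the patient's general health on a Visual Analog Scale (VAS) of 100 mm in the appropriate box on Form B". The corresponding box on Form B is a disease-activity VAS from 0 to 100 mm, and the formula there ends "0.70*LN(ESR/CRP) + 0.014*VAS". In the SAP, Data Listing 21 ("DAS28 by Patient Data Listing") has a VAS column whose heading, although broken in the text available, reads as a patient global VAS in mm.

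**The conflicting statement.** Protocol 8.3.5.2 describes a 10-cm line anchored at no pain and scored 0 to 100. It then says: "This assessment will be used as an input parameter for DAS28 score (Section 8.3.2) and ACR Response Criteria (Section 8.3.4".

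**The global item.** The patient global assessment in Protocol 8.3.5 is a 0 to 10 scale in steps of 0.5. Its stated use is: "This assessment will be used as an input parameter for CDAI score (Section 8.3.3) and ACR Response Criteria (Section 8.3.4". DAS28 is not mentioned.

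**Where DAS28 is used.** Inclusion criterion 5 reads in part "The subject has moderate to severe RA as determined by a 28-joint disease activity score (DAS28) of" at least 3.2; it mentions a VAS without saying which. SAP 4.1.1.2 classes a patient as improved on DAS28 when the score changes by more than 1.2. SAP 4.2.3 plans DAS28 concordance tables and Kendall correlations of imaging change with DAS28 change.

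**The concern.** Section 8.3.5 is where the protocol assigns each instrument to the composites that it feeds. Read on its own, it gives DAS28 to pain and withholds it from the patient global item. Sections 8.3.2 and Appendix 3 do the opposite. No passage says which governs, and Protocol 3.2 requires strict adherence to all of them.

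Pain and global health are different ratings, and one patient can score them differently on the same day. If some of the planned sites (up to 50) enter pain and others enter global health, DAS28 is not one measure across the study. The online calculator named in 8.3.2 standardises the arithmetic but not the choice of item. The SAP has no DAS28 derivation rule that would settle it.

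At stake are the entry criterion for patients close to 3.2, the DAS28 response classification and the DAS28 correlations.

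**Working it through.** The plan states no figure that depends on this point, so there is nothing to reproduce. The check sets the passages side by side and then applies the protocol's own formula.

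**1. Which item feeds DAS28**

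| Place | Item | Scale | Linked to DAS28? |
|---|---|---|---|
| Protocol 8.3.2 | Global health | VAS | Yes |
| Protocol Appendix 3, step 3 and Form B | General health / disease activity | 0-100 mm | Yes |
| SAP Data Listing 21 | Patient global | mm | Yes |
| Protocol 8.3.5.2 | Pain | 0-100 mm | Yes |
| Protocol 8.3.5, patient global | Patient global | 0-10 in steps of 0.5 | No (CDAI and ACR) |
| Protocol Appendix 6, HAQ-DI health item | Overall health | 0-100 | No link stated |

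Three places agree on a non-pain item and one names pain. No global item described in 8.3.5 is linked to DAS28.

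**2. Effect on a single score**

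Formula (Protocol 8.3.2): DAS28 = 0.56√TJC + 0.28√SJC + 0.70 ln(ESR) + 0.014 VAS.

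Replacing global health by pain shifts the score by 0.014 × (pain − global):
- 10 mm: 0.014 × 10 = 0.14
- 20 mm: 0.014 × 20 = 0.28
- 30 mm: 0.014 × 30 = 0.42

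**3. Eligibility at 3.2**

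With a 20 mm gap, the patients who can change status are those whose global-based DAS28 lies within 0.28 of the cut-off:
- If pain is higher, scores from 3.20 − 0.28 = 2.92 up to 3.20 become eligible.
- If pain is lower, scores from 3.20 up to 3.20 + 0.28 = 3.48 become ineligible.

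Example with assumed values TJC 2, SJC 1, ESR 12. The non-VAS part is 0.792 + 0.280 + 1.739 = 2.811.
- VAS 20: 2.811 + 0.280 = 3.09, not eligible.
- VAS 40: 2.811 + 0.560 = 3.37, eligible.

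**4. Response (change above 1.2)**

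The error in the change score is 0.014 × (gap at baseline − gap at follow-up). A gap of 20 mm at both visits gives 0.014 × (20 − 20) = 0. Only a gap that moves between visits matters.

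Example with assumed values: baseline TJC 10, SJC 8, ESR 30; follow-up TJC 6, SJC 4, ESR 20; both VAS items at 60 mm at baseline. The non-VAS fall is 4.944 − 4.029 = 0.915.
- The item falls 20 mm: 0.915 + 0.280 = 1.195, not improved.
- The item falls 30 mm: 0.915 + 0.420 = 1.335, improved.

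So if global health fell 20 mm and pain fell 30 mm, the choice of item alone would decide the classification.

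**5. Correlations**

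Kendall's coefficient depends on ranks. A shift in DAS28 change that is the same for every patient leaves it unchanged. It moves only if the change in the pain-global gap differs between patients enough to reorder them.

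**6. Endpoints not built on DAS28**

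The co-primary endpoints and the key secondary endpoint use Week 24 ACR50 (Protocol 9.3.1, 9.3.2, 9.4). Pain is a proper component of ACR50 (Protocol 8.3.4, Appendix 5). The item chosen for DAS28 does not enter their calculation.

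**The case against.** The best counter-argument is that this is a drafting slip. The DAS28 section, its scoring form and the SAP listing all point to global health. Section 8.3.2 sends the user to Appendix 3, not to 8.3.5.2, and Form B supplies a 0-100 mm box that is not pain. Staff who score DAS28 from that form would enter the right item. This stands as a reason to expect that many sites will do so. It does not remove the contradiction, because 8.3.5.2 is operative text and nothing ranks it below the form.

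Three stronger readings are tempting, and the documents do not support them.

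- **A 0-10 score entered in the mm term.** A reader might infer that sites will put the 0-10 patient global score straight into DAS28. No passage prompts this: that item is assigned to CDAI and ACR, and Form B is marked 0-100 mm. It would also be wrong to compare the resulting error at one visit with the 1.2 threshold, which applies to change between visits.
- **The severity subgroup.** A reader might infer that the moderate/severe subgroup inherits the error. Protocol 9.5.2 and SAP 2.2.1 name no instrument or cut-off for it, and SAP Table 3 includes a mild category. Only inclusion criterion 5 ties moderate to severe disease to DAS28, so the link is an inference.
- **The main result.** A reader might take response to mean the primary reference standard. That standard is ACR50. DAS28 response is secondary and outside the gated tests.

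**Conclusion.** The contradiction is real and unresolved, and a site following 8.3.5.2 as written obtains a wrong DAS28. The size is 0.014 per mm of difference between pain and global health, or 0.28 for an assumed 20 mm gap.

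The reach is limited:
- eligibility for patients near 3.2;
- the secondary DAS28 response, where the gap differs between visits;
- the DAS28 correlations, where the change in gap differs between patients.

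The co-primary and key secondary endpoints are affected only indirectly, through who is enrolled. Sample size is unaffected. The patient values in the examples are assumptions. The documents give no joint distribution of pain and global health, so the share of patients reclassified cannot be estimated. The point should be corrected, but it does not threaten the main analysis.

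**What to change.** Reconcile Protocol 8.3.5.2 with 8.3.2 and Appendix 3:

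1. In 8.3.5.2, delete DAS28 from the stated uses of the pain VAS and keep ACR.
2. In 8.3.2, name the single patient global-health item that feeds DAS28 at screening and Visits 4, 6 and 8, and state its 0-100 mm scale. List DAS28 among that item's uses wherever the item is described.
3. Only if the 0-10 patient global item is the one named, state explicitly that it is multiplied by 10 before it enters the formula.
4. State the same item and scale in the SAP, and settle this before database lock so that the choice cannot follow the results.

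The cost is a few sentences in the protocol and one in the SAP. If the 0-10 item is chosen, no new data are needed, because CDAI, which contains it, is collected at the same visits as DAS28. If a separate mm-scale item is chosen, the sponsor should confirm which item sites have recorded so far.

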8.3.5.3 Patient Assessment of Physical Function (HAQ-DI[©])

Patient assessment of physical function will be evaluated using the Health Assessment Questionnaire Disability Index (HAQ-DI[©]) at screening (up to 30 days before imaging Visit 2) and Visits 4, 6, and 8 (up to 7 days before imaging visits 4, 6, and 8). This evaluation includes questions about functional ability, fine movements of the upper extremity, locomotor activities of the lower extremity, and compound activities requiring both extremities. It also includes assessments of various functional activities such as dressing, rising, eating, walking, etc. Responses are scored on a 0 (no disability) to 3 (completely disabled) scale (Bruce 2003). See Appendix 6 for more information.

8.3.5.4 Acute-phase Reactant

ESR and CRP will be obtained in the RA-specific laboratory panel (see Table 4) at screening and Visits 4, 6, and 8. ESR is used in the calculation of the ACR response level.

8.3.5.5 Widespread Pain Index

Assessment of widespread pain will be evaluated using the widespread pain index (WPI) at screening (up to 30 days before imaging Visit 2) and Visits 4, 6, and 8 (up to 7 days before imaging visits 4, 6, and 8). Providers will assess 19 areas of widespread pain over the last 7 days and will add the total number of areas in pain for the WPI score (score range 0 to 19). This assessment will be used as an additional pain assessment tool to evaluate central pain.

8.4 Image Acquisition

8.4.1 Planar Scintigraphy

Planar spot views of the hands and wrists will be acquired beginning 60 to 75 minutes post injection at Visits 2 and 4. Images and results derived from the images are investigational and should not be used for clinical decision making or shared with the participant.

8.4.2 Tilmanocept Uptake Value (TUV)

TUV is a quantitative imaging metric used to characterize the amount of CD206 activity on planar imaging. Results from prior Phase 1 and 2 studies have demonstrated that TUV is a sensitive and specific predictor of visually interrogated Tc 99m tilmanocept localization in joint regions with presumed inflammatory macrophage activity. A per-joint TUV (TUV_{joint}) relative ratio will be calculated for the each of the 22 DAS-28 joints located in the hands and wrists. A subject-level global TUV (TUV_{global}) assessed across the 22 joints will be used as an indication of overall disease burden.

For all subjects, delegated trained imaging scientists blinded to all clinical subject information will perform semi-automated ROI drawing on planar images of the bilateral hands and wrists to derive relevant count statistics, which are input parameters for TUV_{joint} and TUV_{global}. TUV metrics are further described in the NAV3-33 Statistical Analysis Plan.

8.5 Adverse Events

8.5.1 Definition of Adverse Event

The definitions below follow International Conference on Harmonization (ICH) – Good Clinical Practice (GCP) (see also ICH E2A Guideline for Clinical Safety Data Management: Definitions and Standards for Expedited Reporting).

Adverse Event (AE)

An AE is defined as any untoward medical occurrence in a subject administered a pharmaceutical product and which does not necessarily have a causal relationship with this

treatment. An AE can therefore be any unfavorable and unintended sign (including an abnormal laboratory finding), symptom, or disease temporally associated with the use of a medicinal (investigational) product, whether or not considered related to the medicinal (investigational) product.

Any clinically significant change in a condition (worsening) from screening that results in a change in subject management will be considered an AE and will be recorded on the AE page of the CRF.

By definition for this study, all untoward medical occurrences beginning on the day of Visit 2 Baseline (Day 0) through the final visit (Visit 8) are to be reported as AEs. AEs continuing after study completion will be followed to normalization or stabilization. Additionally, untoward medical events occurring prior to the day of Tc 99m tilmanocept administration will be collected and added to the subject's medical history unless they are related to a study procedure in which case the event will be recorded as an AE. SAEs will be reported from the time of consent through the end of participation.

8.5.2 Categories for Adverse Event Assessment

All AEs will be assessed and documented by the investigator according to the categories detailed below.

Seriousness

For each AE, the seriousness must be determined according to the criteria given in Section 8.5.5.

Severity

The severity of an AE is classified according to the following categories, taking into account the possible range of the intensity of the event:

- Mild The adverse event is transient and easily tolerated by the subject.
- Moderate The adverse event causes the subject discomfort and interrupts the subject's usual activities.
- Severe The adverse event causes considerable interference with the subject's usual activities and may be incapacitating or life-threatening.

Specific drug treatment

Any specific drug treatment will be documented.

Causal relationship to investigational product

The investigator will use the following definitions to assess the relationship of the adverse event to the use of investigational product:

Definitely related: Event can be fully explained by administration of the investigational

product.

Probably related: Event is most likely to be explained by administration of the

investigational product rather than the subject's clinical state or

other agents/therapies.

Possibly related: Event may be explained by administration of the investigational

product or by the subject's clinical state or other agents/therapies.

Probably not related: Event is most likely to be explained by the subject's clinical state or

other agents/therapies, rather than the investigational product.

Definitely not related: Event can be fully explained by the subject's clinical state or other

agents/therapies.

For causality assessments, events meeting the categories of definitely, probably, or possibly related will be considered to be related to investigational product.

Causal relationship to study procedure

The investigator will use the following definitions to assess the relationship of the adverse event to study procedure:

Definitely related: Event can be fully explained by the study procedure.

Probably related: Event is most likely to be explained by the study rather than the

subject's clinical state or other agents/therapies.

Possibly related: Event may be explained by the study procedure or by the subject's

clinical state or other agents/therapies.

Probably not related: Event is most likely to be explained by the subject's clinical state or

other agents/therapies, rather than the study procedure.

Definitely not related: Event can be fully explained by the subject's clinical state or other

agents/therapies.

For causality assessments, events meeting the categories of definitely, probably, or possibly related will be considered to be related to study.

